1.3.2 RATIONALE FOR THE TRIAL

Ublituximab has been studied extensively in the treatment of B-cell malignancies and has been shown to be a potent B-cell depleting agent. Based on the success of other CD20s in the treatment of RMS, ublituximab is being studied in RMS.

TG Therapeutics has performed a phase 2a clinical trial using ublituximab as a single agent to examine the level of B cell depletion by ublituximab as well as determine the optimal dose and infusion time for ublituximab in subjects with RMS. Based on the results of the Phase 2a study with a dosing of 150 mg (infused for 4 hours) on Week 1 Day 1 and a dosing of 450 mg (infused for 1 hour) on Week 3 Day 15, a median of >99% B cell depletion was achieved on Week 4 and sustained until Week 24. The dosing regimen was well tolerated by the subjects with Infusion Related Reactions (grade 1 and 2) being the commonly reported adverse event.

TG Therapeutics also performed a phase 1 clinical study using ublituximab as a single agent to examine the safety and tolerability of a single dose ublituximab at 450 mg in subjects diagnosed with acute Neuromyelitis Optica relapse. Although the single dose of 450 mg ublituximab infused for 4 hours was safe and well tolerated, the study demonstrated that after 3 months, B cells started to replete after being deplete for >99% upon the initial administration of ublituximab on Week 1 Day 1.

In examining the results from both the Phase 2a RMS and Phase 1 acute NMO clinical studies, it is believed that a higher dose of ublituximab will be needed during the initial 6 months of treatment in RMS subjects. With enhanced potency over first generation anti-CD20s due to its glycoengineering, we believe we may be able to optimize the therapeutic window and/or safely decrease infusion times, offering subjects comparable efficacy with a more convenient infusion.

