4.4.1 MS RELAPSE DURING THE STUDY

MS Relapses During the Study

Subjects enrolled into the study will be closely monitored through the study course by the Site and Sponsor's personnel as well as by an external independent Data Safety Monitoring Board (DSMB) to ensure subjects' welfare.

Relapses that occur after study drugs are withdrawn will be assessed over the remainder of the study period and this data will be utilized as part of additional sensitivity analysis (described in the statistical plan) as long as the subject has not withdrawn their consent to be in the trial.

The confirmation of a protocol-defined relapse will be determined by the Independent Relapse Adjudication Committee (IRAP). The steps for confirming a relapse are as follows:

1. Subject Reported Relapse

Subjects who experience new or worsening neurologic symptoms are instructed to contact the Treating Neurologist within 48 hours of symptom onset. All new or worsening neurological events, reported at a visit or over the phone, consistent with MS representing a clinical relapse as assessed by the subject will be initially reported to the Treating Neurologist. In parallel, the Examining Neurologist will also be notified to perform additional assessments. Upon the notification to the Treating Neurologist, the time and date of suspected subject reported relapse will be documented in the dedicated page eCRF (subject reported) by the Treating Neurologist or designee.

The following should be recorded in the eCRF (subject reported) by the Treating Neurologist or designee:

- Date and time of symptom onset as reported by the subject
- Symptoms and events reported by the subject (both neurological and non-neurological)
- Date of initial contact by subject
- Time of initial contact by subject

Within 7 days of the subject reporting the suspected relapse to the Treating Neurologist, the subject will be scheduled and assessed by both the Treating and Examining Neurologist independently.

2. Initial Assessment of Relapse by Treating Neurologist and Examining Neurologist

The Treating Neurologist will perform a neurological and physical examination and safety assessment. The Treating Neurologist or designee will document in the eCRF the following:

- Time and date of neurological and physical examination
- Clinical findings of neurological and physical examination
- Review of previously documented concomitant medications and medical history

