- Safety assessment, including vital signs, CBC, B-cell count, lymphocyte counts, fibrinogen, quantitative immunoglobulin

Subjects with suspected clinical relapses reported to the Treating Neurologist or designee will be referred to the blinded Examining Neurologist who will use Neurostatus to assess the EDSS independently of the Treating Neurologist.

The Examining Neurologist or designee will document in the eCRF the following:

- Date and time of assessment
- EDSS score
- FS Scores

In addition, subjects may not begin IV methylprednisolone (IVMP) treatment of a relapse until the Examining Neurologist has completed his/her examination.

Treatment of relapses may proceed at the discretion of the Treating Neurologist only after the Examining Neurologist has completed his/her exam. The Treating Neurologist will not know the results of the EDSS assessment. When making determination to treat a potential acute relapse the Treating Neurologist can use IVMP (1.0 g/day for at least 3 days and can be extended to 5 days) and will not affect the subject eligibility to continue in the study.

The subject must re-consent at the time of each IRAP-confirmed or Treating Neurologist medically confirmed relapse to continue.

The findings from either the Treating Neurologist and Examining Neurologist will not be shared. The Examining Neurologist must be blinded to the Treating Neurologist's assessment and vice versa.

Following the completion of assessments by the Treating and Examining Neurologists these results will be sent independently to the IRAP.

3. Confirmation of Relapse by IRAP

All assessments entered into the eCRF from both the Treating Neurologist and the blinded Examining Neurologist, will be sent to an Independent Relapse Adjudication Panel (IRAP). IRAP adjudicates each case based on all available data provided for that case and members are not permitted to contact the site or the sponsor for additional information. The IRAP will, in turn, make the final determination of whether the neurological events meet the criteria for a protocol-defined relapse.

Each episode of relapse must be confirmed by the IRAP, based on the neurological assessments performed by the Treating and/or Examining Neurologist independently by documenting either of the following:

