- a. In order to assess teriflunomide compliance, four plasma samples will be taken from all subjects. The first sample will be taken prior to oral administration of teriflunomide or oral placebo on Week 1 Day 1. The second sample will be taken prior to infusion of ublituximab or IV placebo on Week 48. The third sample will be taken at Week 96, prior to first dose of accelerated teriflunomide elimination procedure which begins at Week 100. The last plasma sample for teriflunomide will be taken at Week 116 following the accelerated teriflunomide elimination procedure with either active charcoal or cholestyramine. For subjects who withdraw from treatment early, a blood sample will be collected at the Early Withdrawal from Treatment Visit prior to first dose of accelerated teriflunomide elimination procedure.
 - b. Only plasma samples from subjects treated with teriflunomide will be analyzed for plasma teriflunomide concentrations. See the Laboratory Manual for PK collection and processing instructions.
11. Liver function panel: SGOT/AST, SGPT/ALT, serum gamma-glutamyl transferase (SGGT), total bilirubin, direct/indirect bilirubin. Samples will be taken for analysis as directed in the schedule of assessment (Tables 5, 6, and 7) and as shown in bullet number 2 (Serum Chemistry)
12. Pancreatic enzyme panel: serum amylase and lipase. Samples will be taken for analysis as directed in the schedule of assessment (Tables 5, 6, and 7) and as shown in bullet number 2 (Serum Chemistry)
13. Urinalysis panel for routine safety will be sampled as follows at screening, and Week 1 Day 1 (pre-dose), Day 2, Day 8, Week 3 Day 15 (pre-dose), and Weeks 4, 8, 12, 16, 20, 24 (pre-dose), 36, 48 (pre-dose) 60, 72 (pre-dose), 84, 96, 100 and 104. The urine is to be analyzed for the following pH, ketones, protein, glucose, blood, urobilinogen, bilirubin, microscopic sediment, specific gravity and leucocyte esterase. Additionally, a sample should be obtained for subjects who withdraw from treatment early or have an Unscheduled Relapse Visit.
14. B lymphocyte cell counts (% CD19+ B cells). Samples will be taken for analysis at screening, and Week 1 Day 1 (pre-dose), Day 2, Day 8, Week 3 Day 15 (pre-dose), and Weeks 4, 8, 12, 16, 20, 24 (pre-dose), 36, 48 (pre-dose) 60, 72 (pre-dose), 84, 96, 100 and 104. Additionally, B lymphocyte cell counts will be analyzed for subjects who withdraw from treatment early or have an Unscheduled Relapse Visit.

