15. At screening the following assessments will be performed: HIV, HCV, HBV, Varicella

Note, the study site staff will remain blinded to the results of the PK, ADA and teriflunomide concentration analysis for all subjects. The study site staff will also remain blinded to the results of the B lymphocyte cell counts (% CD19+ B cells) from Week 1 Day 1 onwards.

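### The relapse procedure has the Treating Neurologist document the B-cell count in the eCRF, which conflicts with the site blinding in Protocol 6.2 and is not expressly kept out of the IRAP dossiers

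*Protocol*

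**What the plan says.** **Relapse procedure.** Protocol 4.4.1 step 2 introduces a list with "The Treating Neurologist or designee will document in the eCRF the following". One item on it is "Safety assessment, including vital signs, CBC, B-cell count, lymphocyte counts, fibrinogen, quantitative immunoglobulin". Step 3 continues: "All assessments entered into the eCRF from both the Treating Neurologist and the blinded Examining Neurologist, will be sent to an Independent Relapse" Adjudication Panel. The synopsis, Protocol 6.3.1 and SAP 2.1.3.1 (steps 2 and 3) carry the same instructions.

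**The sample.** Protocol 6.2, item 14, confirms that the test is done at the relapse visit: "Additionally, B lymphocyte cell counts will be analyzed for subjects who withdraw from treatment early or have an Unscheduled Relapse Visit".

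**Site blinding.** The note closing Protocol 6.2 says that "study site staff will also remain blinded to the results of the B lymphocyte cell counts", with effect from Week 1 Day 1. It makes no exception for relapse visits. The same note masks PK, ADA and teriflunomide concentrations. It does not mention CBC lymphocytes or immunoglobulins.

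**Adjudication.** Protocol Appendix D and SAP Appendix A describe a blinded IRAP that works from case dossiers prepared by the CRO. The contents named are the relapse listing (including whether methylprednisolone was given), vital signs, related adverse events, physical examination, EDSS with Neurostatus data, and history. No laboratory result is named and none is excluded. The additional check for unblinding information covers text fields for adverse events and physical examination.

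**The concern.** The B-cell count is the pharmacodynamic marker of ublituximab. Protocol 1.3.2 reports from the Phase 2a study that "a median of >99% B cell depletion was achieved on Week 4 and sustained until Week 24", and the masking in 6.2 shows that the sponsor itself regards the result as able to unblind. An instruction that puts this result in the hands of the Treating Neurologist, at the visit where a suspected relapse is worked up, runs against that masking.

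The Treating Neurologist is close to the primary endpoint in several ways:

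- The neurological findings entered by this person go to the IRAP, which under 4.4.1 step 3 may rely on assessments by the Treating and/or the Examining Neurologist.
- This person decides on methylprednisolone, and that treatment appears in the dossier.
- Under 4.4.2 this person may medically confirm a relapse. Under 4.4.3 that prompts a reminder that the subject may leave for an approved therapy. The primary analysis (Protocol 8.9.1, SAP 2.4.2) counts relapses and time only up to the last treatment.

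Knowledge of the arm could therefore influence what is recorded, what is treated and how long a subject stays on treatment, even if no laboratory value ever reaches the adjudicators.

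**Working it through.** No arithmetic settles this; it is a question of who sees which data. The check sets the passages side by side.

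1. **Is the Treating Neurologist covered by the blinding in 6.2?** Yes. Protocol 4.1.1 counts both neurologists among the site staff, and the note in 6.2 applies to site staff without exception.

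2. **Does 4.4.1 ask for the result or only for the sample?** The wording names the B-cell count as part of a safety assessment to be documented, next to vital signs and CBC. The natural reading is that a value is entered. The schedule (Tables 5 to 7) speaks of blood collection for B-cell counts, and the Unscheduled Relapse Visit in Appendix F lists sample shipping, which fits recording the sample alone. The text of 4.4.1 does not say which is meant.

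3. **Can both instructions be met?** If a value is meant, no: a site following 4.4.1 breaches 6.2, and a site following 6.2 has no value to enter. If only collection is meant, yes. Because the item stands in four places (synopsis, 4.4.1, 6.3.1, SAP 2.1.3.1), it cannot be put down to a single slip.

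4. **Would a B-cell value reach the IRAP?** Step 3 of 4.4.1, taken alone, sends every eCRF assessment. Appendix D replaces that with a selected, blinded dossier prepared by the CRO. Its named contents hold no laboratory result, but the list is not stated to be complete, no laboratory field is excluded, and the extra checks do not mention laboratory data. Exposure is therefore neither prescribed nor ruled out. Protocol 4.2.3 refers to an IRAP Charter that could settle it.

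5. **How informative would a value be?** Entry requires B cells of at least 5% of lymphocytes (Protocol 3.1, item 7), and the Phase 2a median depletion exceeded 99%. A post-dose value would therefore usually point to the arm. The figure is a median, reported from Week 4 to Week 24. The documents give no distribution across individuals and no B-cell data on teriflunomide, so no classification rate can be calculated.

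6. **Does any management rule need the B-cell value at the site?** The laboratory guidance in 5.3 covers neutrophils, platelets, anemia and liver enzymes. None of it depends on a B-cell count.

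**The case against.** The best reply is that the stated design is already sound. Site staff are blinded to B-cell results, samples go to a central laboratory (Protocol 4.1.6), and the IRAP is blinded and reads a prepared dossier. Confirmation rests on FS and EDSS thresholds. The relapse definition requires findings by the Examining Neurologist, whom 4.1.4 blinds to laboratory results, adverse events and earlier EDSS scores. On this view 4.4.1 is loosely worded and nothing leaks.

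Much of that stands, and it limits what may be concluded. Three stronger readings are tempting, and the documents do not support them:

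- **That the arm would be revealed to the adjudicators.** Appendix D and SAP Appendix A describe blinded dossiers without laboratory values. That they do not exclude such values leaves a gap but does not show a leak.
- **That one B-cell value identifies nearly every subject, at the moment the relapse is judged and treated.** The only source is a Phase 2a median reported to Week 24. Nothing says that a central result is back before treatment starts.
- **That the number of relapses measures the damage.** The example rates in Protocol 8.8 give 220 x 1.75 x 0.25 = 96 and 220 x 1.75 x 0.15 = 58, about 154 in all. This is an illustration for an interim pooled rate of 0.20. It counts expected relapses, and says nothing of how many would be unblinded or what bias would follow.

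The reply does not remove the conflict itself. A blinding rule in 6.2 and a documentation rule in four other places point in different directions, and a site must guess which prevails. Nor does the blinding of the Examining Neurologist cover what the Treating Neurologist contributes.

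**Conclusion.** The conflict is real and of moderate severity. Followed literally, the relapse procedure could unblind the Treating Neurologist, against 6.2, at any suspected relapse after dosing. Exposure of the IRAP is a residual risk that rests on an open-ended dossier list and on checks limited to two kinds of text field.

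The size of any bias in the annualized relapse rate cannot be derived from the documents. The conclusion assumes that documenting a B-cell count means entering its value, and that no document outside those supplied (the IRAP Charter, the eCRF specification or the laboratory manual) already masks it. If one does, what remains is a correction of wording.

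A reader might also infer that immunoglobulin results should be masked from the site. The documents give no figure linking immunoglobulin levels to arm, and these results belong to the safety monitoring that 4.1.3 assigns to the Treating Neurologist. That step is not supported.

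**What to change.** - In the synopsis, Protocol 4.4.1 and 6.3.1, and SAP 2.1.3.1 step 2, reconcile the text with 6.2: at a relapse visit the site records only that the B-cell sample was collected, and the result is held centrally and masked.
- In step 3 of the same sections, say that the IRAP receives the dossier defined in Appendix D, in place of all eCRF assessments.
- In Protocol Appendix D and SAP Appendix A, state that B-cell (CD19) and other potentially unblinding laboratory results are excluded from IRAP dossiers. Bring the IRAP Charter into line, or cite it if it already says so.
- Leave CBC and immunoglobulin results available to the Treating Neurologist for safety monitoring.
- Check the eCRF build and the laboratory data transfer to confirm that no B-cell value has been visible at sites or included in a dossier.

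The cost is wording in the protocol and SAP, plus a check, and if needed a change, of the masking settings in the eCRF and central laboratory systems. No visit or sample is added.

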4.4.2 TREATING NEUROLOGIST MEDICALLY CONFIRMED RELAPSE

In suspected relapse events for which IRAP confirmation is pending, may not be logistically possible, and/or complete case profiles for IRAP review are not available, the Treating Neurologist will medically evaluate the suspected relapse event. In these cases, all information from the Treating Neurologist's medical evaluation should still be entered into the eCRF and provided to the IRAP for adjudication. This is to ensure each suspected relapse is documented. Treating Neurologist medically confirmed relapses will not be included in the ARR calculation for the primary endpoint. For any relapse that is Treating Neurologist medically confirmed, subjects should re-consent to continue participation in the trial.

4.4.3 RE-CONSENT CRITERIA AFTER RELAPSING

If a relapse is confirmed by IRAP and/or deemed a Treating Neurologist medically confirmed relapse, the following actions will be taken:

- The subject will be reminded of the current approved MS medications/treatments and the opportunity to terminate the study and be treated with an approved MS medication.
- The subject will be requested to re-sign an informed consent form within 6 weeks after first reporting of the suspected relapse if he/she chooses to continue to participate in the study, in the same treatment assignment.

4.4.4 DISABILITY PROGRESSION

The method of disability progression calculation will be different than that of the relapsed confirmation. The EDSS score will be used to assess disability progression. EDSS assessment will be performed by the Examining Neurologist. The Examining Neurologist must not share the EDSS score with the Treating Neurologist. The scheduled EDSS assessment for disability progression will be performed at screening and on Week 1 Day 1 (prior to randomization) and Weeks 12, 24, 36, 48, 60, 72, 84 and 96. Disability progression is a post hoc analysis only and will not be calculated by the Evaluating Neurologist or other study staff.

Disability progression is defined as an increase of ≥ 1.0 point from the baseline EDSS score that is not attributable to another etiology (e.g., fever, concurrent illness, or concomitant medication) when the baseline score is 5.5 or less, and ≥ 0.5 when the baseline score is above 5.5. Disability progression is considered confirmed when the increase in the EDSS score is confirmed at regularly scheduled visits at least 12 or 24 weeks after the initial documentation of neurological worsening.

4.5 DURATION OF THERAPY

For subjects randomized to ublituximab or treated with IV placebo, infusion will occur on Week 1 Day 1, Week 3 Day 15, and Weeks 24, 48 and 72.

For subjects randomized to teriflunomide or treated with oral placebo, administration may be taken in the morning until the last day of Week 95. Alternative dosing times are allowed if necessary.

If the subject discontinues the study, the reason for study removal and the date the subject was removed must be documented in the eCRF. Subjects who discontinue treatment due to an adverse event should be followed until resolution of the adverse event, unless the event is considered by the Treating Neurologist/PI to be due to the subject's underlying disease.

4.6 SUBJECT RETENTION STRATEGIES

Understanding adherence to pharmacotherapies is crucial in clinical practice and research studies to ensure optimal clinical outcomes and valid study results. Thus, subject adherence can apply to several different clinical trial facets that may include adherence to study procedures, study visit compliance, medications, and adverse event reporting.

For PIs and study site personnel associated with subject recruitment, selection of subjects who understand study burdens and are willing to commit to regimens is a critical up-front step in promoting research adherence. Effective screening is required by the study team to exclude subjects who might reasonably be identified as at risk for non-adherence based on histories of poor adherence with treatments, inconsistency with medical care (lateness or missed appointments), problematic communication or unsure about study participation. Additionally, the study must make sure that the subject will accept random allocation and communicate the importance of study adherence to the subject.

Table 4 (18) below shows different strategies that the study site can employ onto subjects should there be a risk of study adherence:

Table 4. Strategies to employ study adherence

Study adherence risk level	Subject indicators	Retention strategies
Low	No problems scheduling appointments or completing assessment information	Express appreciation of participants' involvement and efforts (routine) Ensure confidentiality of Information provided (routine)

		
Obtain and update contact information (routine)
 
Discuss potential or anticipated barriers to attending appointments (routine)
 
Provide travel/meal reimbursement for study visits, in accordance with local regulation (routine)

Medium	
Concerns about the study medication, behavioral treatment, or procedures
 
Concern that current condition or circumstances could interfere with fulfilling study requirements
 
Reluctant to schedule follow-up appointments due to aforementioned concerns about treatments, circumstances, or conditions
	
Normalize and accept concerns about the study (routine)
 
Continue to provide education/communicate on the disease and treatments to the subject (routine)
 
Remind subject about rationale for study involvement (routine)
 
Provide a range of options to facilitate involvement (non-routine)

High	
Cancels appointments frequently without rebooking, regular no-show, and is unresponsive to contacts for rescheduling appointments
 
Reveals a desire to drop out of the trial
	
Conduct an adherence assessment; that is, learn the participant's explanation for nonattendance or wish to drop out (non-routine)
 
Obtain consensus about risk factors associated with nonadherence (non-routine)
 
Establish priorities for attending to risk factors (non-routine)
 
Identify a range of options for addressing nonadherence (non-routine)
 
Send out letters or emails to participants who are unresponsive to personal contact (non-routine)
 
Delay decision making about dropping out (non-routine)
 
Accept a "no" as temporary and obtain permission to re-contact at a later time (non-routine)

